## 13.3 Adverse event

An AE is any noxious, unintended, or untoward medical occurrence that may appear or worsen in a patient during the course of the study. It may be a new intercurrent illness, a worsening concomitant illness, an injury, or any concomitant impairment of the patients' health, including laboratory test values (as specified by the criteria below), regardless of etiology. Any worsening (i.e. any clinically significant adverse change in the frequency or intensity of a pre-existing condition (documented as medical history)) should be considered an AE. A diagnosis or syndrome should be recorded on the AE page of the eCRF rather than the individual signs or symptoms of the diagnosis or syndrome.

All AEs, regardless of seriousness, severity, or presumed relationship to study drug, must be recorded using medical terminology in the source document and the eCRF. Whenever possible, diagnoses should be given when signs and symptoms are due to a common etiology (e.g. cough, runny nose, sneezing, sore throat, and head congestion should be reported as "upper respiratory infection"). Investigators must record their opinion concerning the relationship of the adverse event to study treatment in the eCRF. All measures required for AE management must be recorded in the source data.

## 13.4 Evaluation of adverse events

A qualified and for this task delegated investigator at the site will evaluate all AEs according the following topics.

## 13.4.1 Seriousness

A serious adverse event (SAE) is any AE that results in any of the following outcomes or actions:

- Results in death;
- Is life-threatening (i.e. in the opinion of the investigator, the patient is at immediate risk of death from the AE). The term "life-threatening" in the definition of "serious" refers to an event in which the patient was at risk of death at the time of the event. It does not refer to an event, which hypothetically might have caused death, if it were more severe.
- Requires inpatient hospitalization or prolongation of existing hospitalization (hospitalization is defined as an inpatient admission, regardless of length of stay);

- Results in persistent or significant disability / incapacity (a substantial disruption of the patients' ability to conduct normal life functions);
- Is a congenital anomaly / birth defect;
- Is considered an important medical AE by the investigator based on medical judgment Important medical adverse events are defined as those occurrences that may not be immediately life threatening or result in death, hospitalization, or disability, but may jeopardize the patient or require medical or surgical intervention to prevent one of the other outcomes listed above. Medical and scientific judgment should be exercised in deciding whether such an AE should be considered serious.

### NOTE:

Events excluded from reporting as SAEs are hospitalizations for:

- A standard procedure for protocol therapy administration. However, hospitalization or prolonged hospitalization for a complication of therapy administration will be reported as an SAE.
- Routine treatment or monitoring of the studied indication not associated with any deterioration in condition.
- The administration of blood or platelet transfusion as routine treatment of studied indication. However, hospitalization or prolonged hospitalization for a complication of such transfusion remains a reportable SAE.
- A procedure for protocol / disease-related investigations (e.g. surgery, scans, sampling for laboratory tests, bone marrow sampling). However, hospitalization or prolonged hospitalization for a complication of such procedures remains a reportable SAE.
- A procedure or hospitalization for progression / relapse investigations (e.g. surgery, scans, sampling for laboratory tests, bone marrow sampling).
- Hospitalization or prolongation of hospitalization for technical, practical, or social reasons, in absence of an AE.
- A procedure that is planned prior to signing informed consent; must be documented in the source document.
- Hospitalization or prolonged hospitalization for a complication remains a reportable SAE.
- Emergency outpatient treatment or observation that does not result in admission, unless fulfilling other seriousness criteria above.
- Sign, symptoms and physical findings indicative of progression of WM are not to be reported as SAE.

If an AE is considered serious, both the AE page of the eCRF and the SAE report form must be completed.

For each SAE, the investigator will provide at least information on severity, start and stop dates, outcome, relationship to IMP and action taken regarding IMP.

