#### 13.7 Reporting of Serious Adverse Events

All events that meet one or more criteria of seriousness that occurred from the time of patient's first application / intake of IMPs up to 30 days after the last study drug intake, regardless the relationship to the study drugs require the completion of a SAE report form in addition to being recorded on the AE page of the eCRF.

A SAE that occurs after this time, if considered related to the study drugs, will be reported regardless of the time between the last drug administration and the event onset.

The investigator shall report serious adverse events to the sponsor / ZKS Ulm without undue delay but not later than within 24 hours of obtaining knowledge by e-mail, using the SAE report form. Where relevant, the investigator shall send a follow-up report to the sponsor (with the same time requirements) to allow the sponsor to assess whether the serious adverse event has an impact on the benefit-risk balance of the clinical trial.

The investigator is required to ensure that the data on these forms is accurate and consistent. This requirement applies to all SAEs (regardless of relationship to study drugs) that occur during reporting period, and those made known to the investigator at any time thereafter that are considered being related to study drugs.

All serious adverse events that have not resolved by the end of the study, or that have not resolved upon discontinuation of the patient's participation in the study, must be followed until any of the following occurs:

- the event resolves;
- the event stabilizes;
- the event returns to baseline, if a baseline value / status is available;
- the event can be attributed to agents other than the study drug or to factors unrelated to study conduct;
- it becomes unlikely that any additional information can be obtained (patient or health care practitioner refusal to provide additional information, lost to follow-up after demonstration of due diligence with follow-up efforts).

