### HA: RRA > RRB

where RRA is the CR / VGPR rate in arm A (Carfilzomib / Ibrutinib) and RRB is the CR / VGPR rate in arm B (Ibrutinib). If the obtained one-sided p-value is less than or equal to 0.1 and the point estimate for the CR / VGPR rate of arm A is larger than that of arm B, it will be concluded that the Carfilzomib / Ibrutinib combination statistically significantly increases CR / VGPR rate compared to single agent Ibrutinib. Additionally, the two-sided 95% confidence interval (CI) of the rate difference (RRA-RRB) will be calculated as effect estimator. Further exploratory analyses of the primary study endpoint encompass the Cochran-Mantel-Haenszel (CMH) test of rate difference adjusting for stratification factors (MYD88 and CXCR4 status and number of prior lines). A CMH 95% stratified confidence interval (CI) of the rate difference (RRA-RRB) with each rate weighted by the number of patients in each stratification factor combination will be calculated as an effect estimator. Additionally, logistic regression models will be used to investigate the influence of putative risk factors on the CR / VGPR rate.

All secondary endpoints will be analyzed exploratory. Group comparisons in binary endpoints will be performed two-sided using the chi square test or Fisher's exact test as appropriate. Additionally, 95% CIs will be calculated for group differences. Survival times will be analyzed using the Kaplan-Meier estimator incl. 95% CI. Furthermore, the Cox Proportional Hazard model will be used to investigate the influence of putative risk factors on survival time. Group comparison in quality of life (ordinal endpoint) will be performed using the Wilcoxon rank-sum test. Additionally, the 95% CI will be calculated for the difference of the medians.

For safety analysis of the RCT, all adverse events will be listed and the frequencies of the most frequent will be calculated. Group comparisons (A vs. B) of frequencies of AEs and SAEs will be performed using the chi square test or Fishers exact test as appropriate.

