4. Progression should be confirmed by a second measurement after 7 to 14 days.

5. Baseline is the IgM value at C1D1.

6. When interrupting ibrutinib, some patients may experience an IgM rebound, which must be carefully differentiated from progression.

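### Section 13.4.1 waives SAE reporting for findings that suggest WM progression, without excepting suspected or uncertain drug cause, and section 13.7 does not mention the waiver

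*Protocol*

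**What the plan says.** Protocol section 13.4.1 defines a serious adverse event by the usual criteria, death and threat to life among them. A NOTE then lists exclusions, introduced as hospitalizations that need not be reported as SAEs. Several bullets carry a limit. The one on routine care, for example, covers "Routine treatment or monitoring of the studied indication not associated with any deterioration in condition". The last bullet is a complete sentence with no limit: "Sign, symptoms and physical findings indicative of progression of WM are not to be reported as SAE".

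Section 13.7 sets the reporting duty. It covers "All events that meet one or more criteria of seriousness that occurred from the time of patient's first application" up to 30 days after the last intake of study drug, and these events, "regardless the relationship to the study drugs require the completion of a SAE report form". It adds the 24-hour deadline and does not mention the NOTE.

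Section 14.3 uses the resulting data: "Group comparisons (A vs. B) of frequencies of AEs and SAEs will be performed using the chi square test" or Fisher's exact test. Section 15 has the DSMC review safety data at two points.

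**The concern.** The bullet turns on whether a finding suggests progression. It does not ask whether a study drug could be the cause. Section 13.4.3 obliges the investigator to judge causality for every AE and SAE, but the bullet does not use that judgement. An investigator who thinks a serious finding looks like WM, and who cannot rule out carfilzomib or ibrutinib, may follow the bullet and send no form. Another investigator with the same case may follow 13.7 and send one. Each can cite the protocol.

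What is at stake is first the safety system. Without an SAE form, the 24-hour notice (13.7) and the sponsor's expectedness and SUSAR assessment (13.7.3) are not triggered. Section 13.1 itself says that the combination is not approved in this indication and calls for closer monitoring of the first arm A patients. Second, the event drops out of the SAE comparison in 14.3. The trial is open label and only arm A receives carfilzomib, so use of the waiver could differ between the arms.

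**Working it through.** The protocol gives no planning figure for the SAE comparison, so there is none to reproduce. The check is mainly a reading of the passages together.

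**1. Conditions on the waiver.**
- Progression criteria exist (Appendix 21.1), with confirmation of IgM progression after 7 to 14 days (footnote 4) and of progression suspected from a single finding within 4 weeks (section 12.2). The bullet refers to none of these.
- A causality judgement exists (13.4.3). The bullet does not refer to it.
- For reports that are filed, 13.7.1 treats a missing causality assessment as related. The bullet has the opposite default: the finding is taken as disease.

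**2. Overlap within the protocol's own lists.** Progression under Appendix 21.1 can rest on clinical features alone, so the WM features in section 10.2 are relevant.

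| WM feature (10.2) | Carfilzomib toxicity |
|---|---|
| Peripheral neuropathy | Neuropathy (Table 7; grade 3 events in the case series in 7.5) |
| WM nephropathy | Acute renal failure (7.5), renal dysfunction (Table 7) |
| Recurrent fever, fatigue | Pyrexia and fatigue as common reactions, pyrexia also among the frequent SAEs (7.5) |
| Low haemoglobin or platelets, immune haemolysis | Anaemia, thrombocytopenia, thrombotic microangiopathy (7.5, Table 7) |

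In the last row the laboratory values fall under another rule (see the objection). The symptoms they cause are what the bullet can reach. Appendix 21.1, footnote 6, shows that the protocol knows progression can be mimicked: "When interrupting ibrutinib, some patients may experience an IgM rebound, which must be carefully differentiated from progression". The bullet does not ask for that distinction.

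**3. What is lost and what is kept.** Lost if the bullet is followed: the SAE form, the 24-hour report, the SUSAR assessment and a place in the SAE comparison. Kept: the AE record (13.3), its grade (13.4.2) and its causality (13.4.3).

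**4. How far the SAE comparison could move (illustration only).** Inputs:
- Arm B SAE rate 43%, the ibrutinib-rituximab figure in section 7.4.
- Arm A SAE rate 60%, an assumption near the 59.9% of the carfilzomib arm of the myeloma trial in 7.5.
- 49 patients per arm (99 planned in total) and a two-sided 5% level, both assumed for this test.
- The share of SAE patients lost to the waiver, an assumption.

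Power = Φ[(d − 1.96·SE0)/SE1], where d = pA − pB, SE0 = √(2·p̄(1−p̄)/49), SE1 = √([pA(1−pA) + pB(1−pB)]/49) and p̄ is the mean of the two rates.

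- No loss: d = 0.60 − 0.43 = 0.17, SE0 = 0.101, SE1 = 0.0995. Power = Φ(−0.28) = 39%.
- 10% of SAE patients lost in arm A only (49 × 0.60 × 0.10 = 2.9 patients): pA = 0.54, d = 0.11. Power = Φ(−0.88) = 19%.
- 10% lost in arm B only (49 × 0.43 × 0.10 = 2.1 patients): pB = 0.387, d = 0.213. Power = Φ(0.15) = 56%.

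Two or three patients can move the observed difference by 4 to 6 points, in either direction depending on the arm that loses them. The calculation also assumes that every SAE of an affected patient is waived. A patient with another reported SAE still counts, so the true shift would be smaller.

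**The case against.** The strongest reply is that leaving disease progression out of SAE reporting is a legitimate design choice, and that 13.4.1 and 13.7 are an exception and a general rule, not a contradiction. The first part stands: true progression need not be an SAE. On the second, an exception works only if its limits are clear and the general rule points to it. Here neither is so.

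The protocol also narrows the gap in ways that stand:
- Laboratory abnormalities that meet a seriousness criterion are reported as SAEs (13.4.8), so thrombocytopenia or a creatinine rise does not escape as a laboratory finding.
- A diagnosis is recorded in place of its signs (13.3), so recognised thrombotic microangiopathy is outside the bullet.
- Waived events remain AEs with grade and causality, AEs are summarised by worst grade (8.5), and the DSMC sees safety data, not SAEs alone.

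A reader might infer three stronger points that the text does not support:
- **That fatal events are exempt.** The NOTE is introduced as a list of hospitalizations, so it is arguable that only the hospitalization criterion is waived. The bullet's form as a full sentence leaves doubt, which is a reason to clarify it and no proof of an exemption.
- **That admissions for transfusion escape in the same way.** That bullet covers only "The administration of blood or platelet transfusion as routine treatment of studied indication", so transfusion for drug-induced cytopenia lies outside it, and it adds: "However, hospitalization or prolonged hospitalization for a complication of such transfusion remains a reportable SAE".
- **That the waiver hides carfilzomib toxicity in arm A.** If arm B has more progression, the waiver may be used more there. Ibrutinib, given in both arms, has its own cytopenias (neutropenia 22%, thrombocytopenia 14% in the pivotal study in 7.4).

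**Conclusion.** The point holds in a limited form. The progression bullet has no exception for suspected or uncertain drug cause, and 13.7 does not acknowledge it. Followed as written, a serious clinical event that resembles WM but may be drug related can miss expedited reporting and the SAE comparison while remaining in the AE data. This rests on the text and on the overlap in the protocol's own lists, not on any assumed rate.

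No size can be given. The illustration depends on an assumed 60% rate and an assumed share waived, and it moves both ways. The SAE test had limited power in any case. The one add-on carfilzomib contrast in the document is 59.9% versus 54.0%, or 5.9 points. A 6-point difference from 43% (49% versus 43%, 49 per arm) gives about 9% power by the same formula with nothing lost. The weight of the point is therefore in expedited safety reporting more than in the test. The primary endpoint is not affected.

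**What to change.** In the NOTE of 13.4.1, replace the last bullet by text to this effect:
- The waiver applies only when the investigator judges the event to be explained by WM progression and not related, under 13.4.3, to either study drug or to its interruption.
- An event of suspected or uncertain drug cause is reported as an SAE within 24 hours, without waiting for confirmation of progression.
- In line with the lead-in of the NOTE, only the hospitalization criterion is waived. Fatal and life-threatening events stay reportable.

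In 13.7, add a reference to the NOTE so that the two sections agree.

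The waiver should not be made to depend on confirmed Appendix 21.1 progression: confirmation takes 7 to 14 days, or up to 4 weeks under 12.2, and the report is due within 24 hours. The judgement at the time of the event, with doubt resolved towards reporting, fits the deadline.

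The cost is an amendment of a few sentences, matching instructions on the SAE form, and a few extra SAE forms, some for events that later prove to be progression.

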#### 13.4.2 Severity

For both AEs and SAEs, the investigator must assess the severity of the event.

The severity of AEs will be graded based upon the patients' symptoms according to the current version of NCI-CTCAE, Version 5.0:

AEs that are not defined in the current NCI CTCAE should be evaluated for severity according to the following scale:

- Grade 1 = Mild transient or mild discomfort; no limitation in activity; no medical intervention / therapy required
- Grade 2 = Moderate mild to moderate limitation in activity, some assistance may be needed; no or minimal medical intervention / therapy required
- Grade 3 = Severe marked limitation in activity, some assistance usually required; medical intervention / therapy required, hospitalization is possible
- Grade 4 = Life threatening extreme limitation in activity, significant assistance required; significant medical intervention / therapy required, hospitalization or hospice care probable
- Grade 5 = Death the event results in death

The term "severe" is often used to describe the intensity of a specific event (i.e. as in mild, moderate or severe myocardial infarction); the event itself, however, may be of relatively minor medical significance (such as severe headache). This criterion is not the same as "serious" which is based on patient / event outcome or action criteria associated with events that pose a threat to a patient's life or functioning. Seriousness, not severity, serves as a guide for defining regulatory obligations.

#### 13.4.3 Causality

The investigator must determine the relationship between the administration of the IMPs and the occurrence of an AE / SAE as not related or related as defined below:

Not related: A causal relationship is unlikely or remote between the AE and study drug administration. Other medications, therapeutic interventions, or underlying conditions provide a sufficient explanation for the observed event.

Related: A causal relationship is possible between the AE and study drug administration. Other medications, therapeutic interventions, or underlying conditions do not provide a sufficient explanation for the observed event.

### 13.4.4 Expectedness / Reference safety information (RSI)

A SAE that is not included in the adverse reaction section of the relevant Reference Safety Information (RSI) by its specificity, severity or outcome is considered an unexpected adverse event. The RSI for this study is the relevant section in the valid IB of Carfilzomib and the relevant section in the valid SmPC of Ibrutinib.

#### 13.4.5 Duration

For both AEs and SAEs, the investigator will provide a record of the start and stop dates of the event.

#### 13.4.6 Action Taken

The investigator will record the action taken with IMP as a result of an AE or SAE, as applicable (e.g. discontinuation or reduction of IMP, as appropriate) and report it in the eCRF or SAE form if concomitant and / or additional treatments were given for the event.

#### 13.4.7 Outcome

The investigator will record the outcome of the event for both AEs and SAEs. All SAEs that have not resolved upon discontinuation of the patient's participation in the study must be followed until recovered / resolved, recovered / resolved with sequelae, not recovered / not resolved (death due to another cause) or fatal (due to the SAE).

## 13.4.8 Abnormal Laboratory Values

An abnormal laboratory value is considered to be an AE if the abnormality is clinically significant in the discretion of the investigator at the site (e.g. results in discontinuation from the study; requires treatment, modification / interruption of IMP dose, or any other therapeutic intervention; or is judged to be of significant clinical importance).

Regardless of severity grade, only laboratory abnormalities that fulfill a seriousness criterion need to be documented and reported as a SAE.

If a laboratory abnormality is one component of a diagnosis or syndrome, then only the diagnosis or syndrome should be recorded on the AE page of the eCRF. If the abnormality laboratory value was not a part of a diagnosis or syndrome, then the abnormal laboratory value should be recorded as an AE.

### 13.5 Pregnancy / Lactation exposure

Any pregnancy / lactation exposure in a female patient or in a female partner of a male patient diagnosed during the treatment period or within 6 months after last study treatment administration must be reported without undue delay but not later than within 24 hours of obtaining knowledge of the events by anyone of the study team members at the site using the study specific pregnancy reporting form to the sponsor / ZKS Ulm. In female study patients IMP must be discontinued in the case of pregnancy / lactation exposure during study treatment. Follow-up information on the patients and her pregnancy / lactation exposure outcome should be communicated by the investigator / site to the sponsor / ZKS Ulm as soon as available.

The investigator / site will follow-up all female patients or female partners of men participating in the study who become pregnant until end of pregnancy. The investigator / site must notify the sponsor of the outcome of the pregnancy / lactation exposure as specified below (follow up report to the initial report). Pregnancy / lactation exposure should be reported on the pregnancy/ lactation exposure report form. If the outcome of the pregnancy / lactation exposure meets the criteria for immediate classification as a SAE (i.e. spontaneous or therapeutic abortion, any congenital anomaly [including that in an aborted fetus], stillbirth, neonatal death, elective abortion due to developmental anomalies), the investigator / site should follow the procedures for reporting SAEs in addition to providing the pregnancy / lactation exposure report form. All neonatal deaths that occur within 30 days of birth should be reported, without regard to causality, as SAEs. In addition, any infant death after 30 days of birth that the investigator suspects as related to the in-utero exposure to the study drug should also be reported as SAE.

The investigator should counsel the patient or the partner of the patient, discuss the risks of continuing the pregnancy / lactation, and possible effects on the fetus or new born. Monitoring of the patient should continue until conclusion of the pregnancy / end of lactation.

Since IMPs may cause fetal harm, female partners of men participating in the study who become pregnant will be asked to sign an ICF and will be monitored for the outcome of the pregnancy as described above.

